10.4 ELECTROCARDIOGRAM

Descriptive statistics for ECG parameters (heart rate, RR interval, PR interval, QRS interval, QT interval, QTcB interval, and QTcF interval) and changes from baseline values at each assessment time point to the end of the DB treatment period will be presented by treatment group. The QTc will be calculated using both the Bazett and Fridericia corrections (if the vendor does not provide).

Electrocardiographic parameter values are considered PCS if they meet or exceed the higher-limit PCS criteria listed in Table 10-4. The number and percentage of participants with PCS postbaseline ECG values will be tabulated by treatment group for the double-blind treatment period. The percentages will be calculated relative to the number of participants with available non-PCS baseline values and at least 1 postbaseline assessment for the double-blind treatment period. The numerator is the total number of participants with available non-PCS baseline values and at least 1 PCS postbaseline value for the double-blind treatment period. A supportive tabular display of participants with PCS postbaseline values will be provided, including the participant identification (PID) number, baseline, all postbaseline (including non-PCS) values, and change from baseline.

In addition, a tabular display showing all AEs that occurred in participants who had postbaseline PCS ECG values will be provided.

A shift table from baseline to the end of study in the Investigator's overall interpretation of the ECG will be presented by treatment group for the following categories: normal; abnormal, not clinically significant; abnormal, clinically significant. A tabular display showing participants with postbaseline clinically significant ECG abnormalities according to the Investigator's overall interpretation will be provided.

Table 10-4 Criteria for Potentially Clinically Significant Electrocardiograms

Parameter	Unit	Higher Limit
QRS interval	msec	≥ 150
PR interval	msec	≥ 250
QTc (QTcB or QTcF) interval	msec	>500
QTc (QTcB or QTcF) interval	msec	Increase of > 60

QTc = QT interval corrected for heart rate.

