6.6.5 Electrocardiograms

A 12-lead ECG will be performed at Visit 1 (Screening) and Visit 6 or ET using a standard paper speed of 25 mm/sec. ECGs will be electronically transmitted for analysis according to the instructions provided by the ECG central reader. Measurements (in msec) will be recorded for the following parameters in lead II or lead III (other leads may be used only if it is not possible to obtain good-quality tracings from lead II or lead III): PR interval, QRS interval, RR interval (preceding the QT), and uncorrected QT interval. Copies of the ECG waveforms will also be sent to the central reader, where the ECG parameters will be measured and evaluated. The ECG tracing and cardiology report will be retained as a source document. Sites will transmit all ECGs to the ECG central reader.

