6.7 Summary of Methods of Data Collection

An IWRS will be used to screen patients, dispense IP, randomize patients, and manage IP inventory. All other data for this study will be collected using eCRFs via an electronic data capture system, except for ECG and laboratory data.

A qualified central ECG and central laboratory vendor will be used for the analysis of all ECGs and blood and urine samples. ECG and laboratory data will be transferred to Allergan or its designee on a periodic basis throughout the study.

7 Statistical Procedures

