7.3.3.4 Electrocardiogram

Descriptive statistics for ECG parameters (ie, heart rate, PR interval, QRS interval, RR interval, QT interval, QTcB, and QTcF) and changes from baseline values at each assessment timepoint will be presented by treatment group.

The number and percentage of patients with PCS postbaseline ECG values will be tabulated by treatment group. The criteria for PCS ECG values will be detailed in the SAP. The percentages will be calculated relative to the number of patients with available non-PCS baseline values and at least 1 postbaseline assessment. The numerator will be the total number of patients with available non-PCS baseline values and at least 1 PCS postbaseline value. A supportive listing of patients with PCS postbaseline values will be provided, including the patient identification number, study center number, and baseline and postbaseline values.

In addition, a listing of all AEs occurring in patients who have PCS ECG values and a listing of patients with clinically significant postbaseline ECG abnormalities, as reported by the Investigator and/or the central ECG laboratory, will also be provided.

The number and percentage of patients with a change from baseline QTc > 30 msec but not exceeding 60 msec, and of patients with an increase > 60 msec will be tabulated by treatment group. A supportive listing that includes the patient identification number, study center number, all QTc values (including change from baseline values), and all AEs will be provided for all patients who have postbaseline QTc changes > 30 msec.

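### SAP 10.4 builds the display of clinically significant ECG abnormalities on the Investigator's reading alone, while Protocol 7.3.3.4 also admits the central ECG laboratory as a source, and the narrowing is not declared

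*SAP*

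**What the plan says.** **Protocol.** Section 7.3.3.4 undertakes to provide "a listing of patients with clinically significant postbaseline ECG abnormalities, as reported by the Investigator and/or the central ECG laboratory". On the natural reading, a report from either source is enough to put a patient on the listing.

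The central reader has a real role in data collection. Section 6.6.5 has sites transmit every ECG to the central reader and states: "Copies of the ECG waveforms will also be sent to the central reader, where the ECG parameters will be measured and evaluated". It also keeps a cardiology report as source. Section 6.7 adds: "A qualified central ECG and central laboratory vendor will be used for the analysis of all ECGs and blood and urine samples". ECG data are transferred periodically to the sponsor or its designee.

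**SAP.** Section 10.4 plans two qualitative ECG outputs. The first is "A shift table from baseline to the end of study in the Investigator's overall interpretation of the ECG", by treatment group, in three categories (normal; abnormal but not clinically significant; abnormal and clinically significant). The second is a "tabular display showing participants with postbaseline clinically significant ECG abnormalities according to the" Investigator's overall interpretation. Neither names the central laboratory.

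The same section also plans descriptive statistics for the ECG parameters, a table and participant display of PCS values by the Table 10-4 limits, and a display of adverse events in participants with PCS values.

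SAP 17.0 records three departures from the protocol: the SF-12 model terms, the adverse event summary time frame and the serious adverse event definition. None concerns ECGs, and neither amendment list in SAP Appendix III mentions an ECG change.

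**The concern.** The protocol names two sources for one cardiac-safety listing and the SAP keeps only one. A programmer who follows SAP 10.4 as written will leave out any patient whose postbaseline ECG was reported as clinically significant by the central laboratory but not by the site. The protocol says such a patient should be listed.

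This matters for two reasons. The trial is global and multicenter, and the central vendor is the one ECG source common to all sites, whereas the Investigator's interpretation is made site by site. In addition, a reader of the study report who relies on SAP 17.0 to learn where the analysis departs from the protocol would not find out that this listing had been narrowed.

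**Working it through.** No arithmetic applies, because the point concerns scope of reporting and the plan gives no figure to reproduce. The check sets the passages side by side.

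**Step 1: source of the clinically significant call**

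| Output | Protocol 7.3.3.4 | SAP 10.4 |
|---|---|---|
| Listing or display of clinically significant postbaseline abnormalities | Investigator and/or central ECG laboratory | Investigator only |
| Shift table of overall interpretation | Not promised | Added, Investigator only |

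The first row is a mismatch. The second is not, since the SAP adds something the protocol never promised.

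**Step 2: is the change declared?** No. It appears neither in SAP 17.0 nor in Appendix III.

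**Step 3: which central findings are still reported?** The parameters are measured centrally (Protocol 6.6.5), and the PCS outputs in SAP 10.4 depend only on parameter values. A participant therefore appears in the PCS display, without any Investigator call, if a postbaseline value meets one of these Table 10-4 limits:

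- QRS of at least 150 msec;
- PR of at least 250 msec;
- QTcB or QTcF above 500 msec;
- an increase in QTcB or QTcF of more than 60 msec.

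**Step 4: what remains?** Cross the two criteria for an abnormality that the central laboratory reports as clinically significant:

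| | Meets a Table 10-4 limit | Meets no Table 10-4 limit |
|---|---|---|
| Investigator also calls it significant | PCS display and Investigator display | Investigator display |
| Investigator does not | PCS display | No display named in SAP 10.4 |

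Only the lower right cell is lost. Table 10-4 covers three intervals and nothing else, so a rhythm or morphology finding would be an example, if the central laboratory reports such findings as clinically significant.

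**Step 5: how many patients?** This cannot be calculated. Neither document gives a rate at which the central laboratory and the Investigator disagree. The number of patients with a postbaseline ECG is not fixed by the documents either. The 15% dropout assumption at Week 6 does not supply it, because the ECG is also scheduled at early termination (Protocol Table 1 and 6.6.5).

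**The case against.** The strongest defense is that this is one phrase in a descriptive listing. It has several parts.

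- **The documents do not show that the central laboratory grades clinical significance.** Protocol 6.6.5 has it measure and evaluate parameters and mentions a cardiology report, but defines no such category. The one place where a named person judges the importance of an ECG finding is inclusion criterion 12, and that person is the investigator. This stands in part. Protocol 7.3.3.4 nevertheless treats the central laboratory as a reporter of such abnormalities. If that was a mistake, SAP 17.0 is the place to say so, and an edit is needed either way.
- **The protocol's and/or is loose.** It is, and it does not commit the sponsor to a separate central-laboratory output. It does include the central laboratory as a qualifying source, and the SAP does not.
- **The data may be listed anyway.** SAP 15.3 says that all assessments go into the data listings, and SAP 3.0 places the output specifications in a separate document that is not available here. This stands against any claim of total absence. However, the SAP 15.3 sentence closes a section on repeated or unscheduled safety assessments and does not mention central interpretations. A full listing of assessments is also not the listing of affected patients that the protocol describes.
- **Important findings have other routes.** A clinically relevant abnormality can be recorded as an adverse event (Protocol 9.1.1), and clinical findings at termination must be followed (Protocol Table 1, footnote b). This stands and limits the weight of the point.

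A reader might go further and infer that abnormalities called only by the central reader appear in no output, or that the standardized reading has been discarded for local ones. The documents do not support either inference. The central measurements still feed the descriptive statistics and the PCS outputs, and the unseen output specifications prevent proof of total absence. A reader might also infer that the SAP owes a shift table on the central interpretation. It does not, because the protocol promises no shift table from any source.

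**Conclusion.** The point holds in limited form. SAP 10.4 is narrower than Protocol 7.3.3.4 on the source of clinically significant ECG abnormalities, and the difference is undeclared. The loss is confined to abnormalities that only the central ECG laboratory reports as clinically significant and that meet no Table 10-4 limit. These have no named display in the SAP.

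Its size in patients is unknown and cannot be bounded from the documents. No efficacy estimate, test, PCS count or adverse event table changes. It is a modest correction to a cardiac-safety listing, worth making because it is specific and cheap.

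The conclusion assumes that either source qualifies a patient under the protocol's wording, and that the separate output specifications follow the SAP text. Whether any patient is actually lost depends on the central laboratory supplying a clinical-significance call, which the sponsor can establish from the vendor's data specification.

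**What to change.** In SAP 10.4, widen the display of clinically significant postbaseline ECG abnormalities so that a report from the Investigator, the central ECG laboratory or both places a participant in it. Add a column for the source of the call.

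If the central laboratory does not supply such a call, keep the display as it is, but declare in SAP 17.0 that the protocol's second source has been removed and give the reason.

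The cost is one revised sentence and one listing column in the first case, or a short entry in SAP 17.0 in the second. Protocol 6.7 says that ECG data are already transferred to the sponsor or its designee. Whether a central significance call is among the transferred fields should be checked first. The Investigator-based shift table can stay unchanged.

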10.5 OTHER SAFETY PARAMETERS

Other safety parameters include YMRS, EPS scales (AIMS, BARS, and SAS scores) and C-SSRS.

10.5.1 YMRS Scale

The number and percentage of participants with treatment-emergent mania will be presented by treatment group. Treatment-emergent mania will be defined as an YMRS total score of 16 or greater at any postbaseline visit. Descriptive statistics for YMRS total score and change from baseline values at each assessment time point will be presented by treatment group.

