improvements in tolerability. In the phase III bipolar depression program, all patients were started on cariprazine 1.5 mg. Patients assigned to 1.5 mg remained on dose for the remainder of the study, whereas, patients assigned to cariprazine 3 mg remained on cariprazine 1.5mg for 14 days before being uptitrated to 3 mg for the remainder of the study. Accordingly, based on the above-mentioned studies in MDD and bipolar depression, the doses for investigation in Study 3111-302-001 will be 1.5 mg/day and 3 mg/day as an adjunctive treatment to ADT.

Another area to consider is dopamine D2/D3 receptor occupancy. Cariprazine 1.5 mg/day D2 occupancy is 59% while its D3 occupancy is 83%. At 3 mg/day, D2 occupancy for cariprazine is 72% and D3 is 90% (Study RGH-PK-15). While no specific occupancy data are available to guide a dosing decision for adjunctive use of an antipsychotic agent with antidepressants, we do know that 2 other dopamine partial agonists with approved indications as an adjunctive treatment to antidepressants (aripiprazole 5 to 15 mg/day and brexpiprazole 2 mg/day to 4 mg/day) have rates of D2 receptor occupancy ranging from 60% to 90% (aripiprazole 80% to 90%; brexpiprazole 60% to 67%). The low D2 occupancy of cariprazine at 1.5 mg/day and 3 mg/day may provide enough receptor blockade to affect mood without adversely affecting movement. The occupancy of D3 and 5HT_{1A} receptors may also play an important role in the antidepressant efficacy of cariprazine.

Study Duration: The study will consist of up to 14 days of screening (with up to an additional 7 days if needed with Sponsor approval) and washout of prohibited medications followed by 6 weeks of DB treatment followed by a 4-week safety follow-up.

Screening/Washout Period: Patients with MDD with inadequate response to ongoing ADT in the current episode will undergo a screening period where consent, eligibility assessment, and withdrawal of prohibited medications will occur for up to 14 days (with up to an additional 7 days if needed with Sponsor approval). During the screening period, the patients will continue to take the ADT at the same dose to which they are having an inadequate response. Patients who are taking more than one antidepressant at Screening, regardless of the indication, will need to discontinue all other antidepressants prior to Baseline (Visit 2).

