4.4 Exclusion Criteria

The following are criteria for exclusion from participating in the study:

1. Diagnosis of any current psychiatric diagnosis other than MDD (including those with current intellectual development disability) with the exception of specific phobias
2. History of manic or hypomanic episodes
3. Patients with a YMRS score ≥ 12
4. Patient has a history of meeting DSM-5 diagnosis for any substance-related disorders (ie, use disorders except caffeine- and tobacco-related) within the 3 months before Visit 1 (Screening)
5. Patient had a positive result at Visit 1 (Screening) from the urine drug screen (UDS) for any prohibited drugs. Exception: patients with a positive UDS at Visit 1 for opiates, cannabinoids, amphetamines, barbiturates, or benzodiazepines may be allowed in the study provided:
 - a. The drug was used for a legitimate medical purpose;
 - b. The drug can be discontinued prior to further participation in the study (except for benzodiazepines which may be continued if the patient has been taking a stable dose [ie, lorazepam up to 2 mg/day or its benzodiazepine equivalent] for at least 1 month prior to Visit 1 (Screening) or if used as rescue during washout); and

- c. A repeat UDS must be performed prior to Visit 2 and must be negative, except benzodiazepine use as described in 4(b) and Section 4.5.3
- 6. The patient represents a suicide risk, as determined by meeting any of the following criteria:
 - a. Patient made a suicide attempt within the past year prior to Visit 1 (Screening)
 - b. Patient had a score of 4 or greater on Item 10 of the MADRS at Visit 1 (Screening) or Visit 2 (Baseline)
 - c. Patient had a score of 3 or greater on Item 3 of the HAMD-17 at Visit 1 (Screening) or Visit 2 (Baseline)
 - d. Patient is at significant risk, as judged by the investigator, based on the psychiatric interview or information collected in the Columbia–Suicide Severity Rating Scale (C-SSRS) at Visit 1 (Screening) or Visit 2 (Baseline)
- 7. Patient is at imminent risk of injuring self or others or causing significant damage to property, as judged by the investigator
- 8. Patient has a history of intolerance or hypersensitivity to cariprazine or other drugs of the same class or to rescue medications

Treatment-Related Criteria:

- 9. Per ATRQ, patient failed to respond to > 3 trials of ADTs given at an adequate dose (as defined by the ADT package insert) and duration of ≥ 6 weeks during the present episode

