6.6.6.3 Young Mania Rating Scale

The YMRS ([Young et al, 1978](#)) is an 11-item scale that assesses manic symptoms based on the patient's perception of his or her condition over the previous 48 hours, as well as the physician's clinical observations during the interview. The 11 items are elevated mood, increased motor activity-energy, sexual interest, sleep, irritability, rate and amount of speech, language-thought disorder, content, disruptive-aggressive behavior, appearance, and insight. The severity of the abnormality is rated on a 5-point (0 to 4) or 9-point (0 to 8) scale. Possible scores range from 0 to 60.

This scale will be administered by a trained rater with expertise in evaluating manic patients.

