8.4.3 Double-blind Treatment Period (Visits 3 to 6/ET)

The following procedures will be carried out during the DB treatment period at every visit except as noted:

- Review concomitant medications and assess ADT compliance
- Collect IP blister cards, perform drug accountability and assess IP compliance
- Assess MADRS, CGI-S, CGI-I, and C-SSRS; HAM-A (Visits 4 and 6/ET only), YMRS (Visit 6/ET only) and HAMD-17 (Visit 6/ET only)
- Evaluate EPS (AIMS/BARS/SAS)
- Administer SF-12 (Visit 6/ET only)
- Collect vital signs measurements (including weight)
- Collect waist circumference measurement (Visit 6/ET only)

- Review and assess AEs and SAEs
- Collect blood sample for serum pregnancy test for women of childbearing potential (Visit 6/ET only)
- Collect blood samples for clinical laboratory determinations (Visit 6/ET only)
- Collect blood for PK evaluation (any time during Visits 4, 5 and 6/ET)
- If not already obtained previously, obtain consent for and collect blood for the pharmacogenetic sample. A single sample can be obtained at any time between Visit 2 and Visit 6/ET, inclusive
- Perform ECG (Visit 6/ET only)
- Perform physical examination (Visit 6/ET only)
- Access IWRS to dispense IP (Visit 3 through Visit 5), and register patient completing Visit 6/ET

Note: After completion of Visit 6/ET, patients will receive treatment for their MDD as deemed necessary by the Investigator or designee.

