8.8 Early Discontinuation of Patients

Patients may discontinue from the study at any time for any reason. Discontinuation is permanent; once a patient is discontinued, he/she shall not be allowed to enroll again.

Patients can be prematurely discontinued from the study and subsequently enter the safety follow-up period for one of the following reasons:

- AE
- Noncompliance with protocol
- Noncompliance with IP dosing regimen and/or ongoing ADT dosing regimen
- Withdrawal of consent (a clear reason must be documented when possible)
- Patient decision to not continue in the study
- Lost to follow-up (every effort must be made to contact the patient; a certified/traceable letter must be sent)
- Study terminated by Sponsor
- Site terminated by Sponsor
- Pregnancy
- Other reasons

Notification of early patient discontinuation from the study and the reason for discontinuation will be clearly documented on the appropriate eCRF page. Patients who take IP during the study and who prematurely discontinue from the study, regardless of cause, should be seen for a final assessment. A final assessment will be defined as completion of the evaluations scheduled for Visit 6/ET. If the patient discontinues after IP is taken, the patient is also expected to return for the Safety Follow-up Visit (Visit 7) 4 weeks after completion of the ET Visit.

At a minimum, the following information should be collected when a patient is discontinued:

1. The reason the patient discontinued
2. The date of the last dose of IP taken by the patient. All IP should also be retrieved from the patient.
3. The date of the last study assessment and/or contact. A follow-up contact (telephone or visit) will be arranged as appropriate

4. (S)AEs

5. Compliance with the IP administration as specified in this protocol

6. Final Assessments: Unless there is withdrawal of consent, every effort should be made to ensure that all procedures and evaluations scheduled for Visit 6/ET and subsequently Visit 7 (Safety Follow-up Visit) are performed ([Table 1](#), and Section [8.4](#)).

Discontinued patients will not be replaced, and re-screening will not be allowed.

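### The treatment-emergent mania row is in effect one YMRS reading at Visit 6/ET: it can miss earlier episodes and is not linked to mania reported as an adverse event

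*SAP*

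**What the plan says.** **Definition.** SAP 10.5.1 and Protocol 7.3.3.5 report treatment-emergent mania as a count and percentage by arm. The rule is: "Treatment-emergent mania will be defined as an YMRS total score of 16 or greater at any postbaseline visit". Adverse events play no part in it.

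**Schedule.** Protocol 8.4.3, on the double-blind visits, has "YMRS (Visit 6/ET only) and HAMD-17 (Visit 6/ET only". Protocol Table 1, SAP Table 3-2 and the COVID-19 schedule (Protocol Table 4) agree. No YMRS is planned at Visits 3, 4, 5 or 7.

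**Recall.** Protocol 6.6.6.3 says the scale assesses "manic symptoms based on the patient's perception of his or her condition over the previous 48 hours", together with what the physician observes at interview.

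**Duration.** Under Protocol Section 3, screening is "followed by 6 weeks of DB treatment followed by a 4-week safety follow-up".

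**Entry.** Exclusion criterion 3 in Protocol 4.4 bars "Patients with a YMRS score ≥ 12", so a later score of 16 or more is new.

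**Early leavers.** Protocol 8.8: "Patients who take IP during the study and who prematurely discontinue from the study, regardless of cause, should be seen for a final assessment". That assessment is the Visit 6/ET set, which includes the YMRS.

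**Adverse events.** They are asked about at every visit (Protocol 9.1.1) and tabulated by system organ class and preferred term (SAP 10.1).

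**The concern.** The definition is worded as if several postbaseline YMRS scores existed. Apart from any unscheduled one, there is a single score. A reader of the table will take the percentage as the share of participants who became manic during six weeks of treatment. What it gives is the share scoring 16 or more in the two days before, and at, the last double-blind visit.

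A participant with a manic episode in Week 3 that has settled by Week 6 is a non-case in this row, even if the episode was recorded as an adverse event. Nothing in SAP 10.5.1 brings the two sources together.

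Other safety flags are handled differently. The SAP plans a display of all adverse events in participants flagged on laboratory values (10.2), vital signs (10.3), ECG (10.4), the EPS scales (10.5.2) and the C-SSRS (10.5.3). It plans none for the mania flag. The EPS scales are also given at every double-blind visit, and EPS adverse events have their own list of preferred terms (SAP 10.1). Mania has neither.

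At stake is the mania count per arm. No primary or key secondary result is affected.

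**Working it through.** The documents state no mania rate or detection figure, so there is no planned number to reproduce. The check has three parts.

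**1. Share of treatment time inside the recall window**

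Inputs: one scheduled postbaseline YMRS (Protocol 8.4.3), recall of 2 days (Protocol 6.6.6.3), treatment of 6 × 7 = 42 days (Protocol Section 3).

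- Completer: 2/42 = 4.8%.
- With the ±3-day visit window: 2/45 = 4.4% to 2/39 = 5.1%.
- With the +7-day COVID-19 extension: 2/49 = 4.1%.
- Early termination at day 7, 14 or 28: 2/7 = 28.6%, 2/14 = 14.3%, 2/28 = 7.1%.

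**2. Chance that an episode touches the window**

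This is a different quantity and needs assumptions that the documents do not supply: a completer, onset uniform over the 42 days, an episode lasting D days, and a score of 16 or more whenever any part of the episode falls in the last 2 days. The chance is then (D + 2)/42.

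| Assumed duration D (days) | (D + 2)/42 | Chance |
|---|---|---|
| 2 | 4/42 | 10% |
| 4 | 6/42 | 14% |
| 7 | 9/42 | 21% |
| 14 | 16/42 | 38% |
| 21 | 23/42 | 55% |
| 28 | 30/42 | 71% |

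The result depends almost wholly on D. An episode still present at Visit 6 or ET always falls inside the window.

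**3. Direction of the error**

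At a fixed threshold, participants scoring 16 or more at one visit are a subset of those who would score 16 or more at some time in the six weeks. The row can equal that period count or be lower. It cannot be higher.

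For the comparison between arms, let p1 and p0 be the true period rates and q the fraction detected, the same in each arm. The table shows q·p1 and q·p0. The difference becomes q(p1 − p0), which is smaller. The expected ratio stays p1/p0.

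**The case against.** The strongest reply is that mania reporting does not rest on this row. Adverse events are asked about at every visit and tabulated by preferred term, severity and relationship. Serious events and those leading to discontinuation are listed. A Week 3 manic episode reported as an adverse event will therefore appear by arm. Severe cases also tend to reach a YMRS: psychiatric hospitalization requires discontinuation (Protocol 8.9), and the ET assessment is then due. Unscheduled examinations are allowed (Protocol 8.6), and the definition would count a YMRS taken at one. All of this stands. It confines the gap to this table, but it does not make the row a six-week count or link it to the adverse events.

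Uniform onset can also be questioned. The 3 mg arm reaches 3 mg only at Week 2. If onset follows exposure, episodes cluster later and detection at Week 6 is better than the table above suggests. That stands too, and is one reason to give no estimate of the shortfall.

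Separate displays for scales and adverse events are the plan's convention: EPS is handled that way. But EPS also gets the listing of adverse events in flagged patients and a grouped term list, so following that convention argues for the additions below.

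Finally, a reader might infer that the plan catches only about 5% of mania. The documents do not support this: 4.8% is the share of treatment time in the recall window, not the share of episodes detected.

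**Conclusion.** The point holds as one of labelling and completeness. The row named treatment-emergent mania is a Visit 6/ET assessment with a 48-hour look-back, covering 2 of 42 treatment days for a completer. It can only match or fall below the six-week count. It probably falls below if some episodes begin and end before the last visit. The shortfall cannot be sized from the documents; the range of 10% to 71% detection rests on assumed durations of 2 to 28 days, uniform onset and completers.

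Two stronger readings go too far. One is that the trial will understate mania. That needs transient episodes to occur, and the documents give neither their rate nor their length; mania reported as an adverse event is also tabulated elsewhere. The other is that the drug–placebo comparison is necessarily blurred. Equal under-detection shrinks the absolute difference but leaves the expected risk ratio unchanged, and the documents give no reason to expect unequal detection.

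This is worth correcting because the remedy uses data already collected and coded.

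**What to change.** In SAP 10.5.1:

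1. Keep the protocol-defined row (YMRS of 16 or more) and label it as assessed at Visit 6/ET plus any unscheduled postbaseline YMRS.
2. Add a row for TEAEs of mania or hypomania, using a preferred-term list fixed before unblinding, as SAP 10.1 already does for EPS.
3. Add a combined row: YMRS of 16 or more, or such a TEAE. Name it mania or hypomania and show it beside its two components, so that the threshold and the reported events are not confused.
4. Add the listing of all adverse events in flagged participants, as for the laboratory, vital sign, ECG, EPS and C-SSRS flags.
5. Record the additions in SAP 17.0, since they go beyond Protocol 7.3.3.5.

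No new visit, assessment or data collection is needed. The cost is some SAP wording, a term list, one extra table and one listing. The downside for the sponsor is that the reported mania rate may be slightly less favourable.
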